### 7.3 Importance of Adverse Event Reporting

Timely and complete reporting of safety information assists BerGenBio in identifying any untoward medical occurrence, thereby allowing:

- safety of study patients;
- a greater understanding of the overall safety profile of the investigational drug;
- recognition of dose-related investigational drug toxicity;
- appropriate modification of study protocols;
- improvements in study design or procedures; and

- adherence to worldwide regulatory requirements.

## 7.4 Evaluating Adverse Events

Following the patient's written consent to participate in the study, AEs occurring after consent, but before treatment, and during treatment and within 30 days after cessation of treatment are collected in accordance with [Section 7.1](#), [Section 7.4.3](#) and [Section 7.5](#).

All identified AEs must be accurately recorded and described on the appropriate AE page of the electronic Case Report Form (eCRF). If known, the diagnosis of the underlying illness or disorder should be recorded, rather than its individual symptoms. The following information should be captured for all AEs: date of onset and resolution, severity of the event (see definitions in [Section 7.4.1](#)), Investigator's opinion of the relationship to IMP (see definitions in [Section 7.4.2](#)), and assessment whether the event was serious or non-serious (see definitions in [Section 7.4.3](#)). In addition, treatment required for the AE, action taken with IMP, information regarding resolution/outcome.

### 7.4.1 Assessment of severity

All AEs (including SAEs) are to be accurately recorded on the AE page of the patient's eCRF. Each event will be graded for severity using the classifications of National Cancer Institute (NCI) Common Terminology Criteria for Adverse Events (CTCAE) v4.03. For events not addressed in the NCI CTCAE v4.03, classifications the following grading will apply:

- **Mild (Grade 1)** - Mild; asymptomatic or mild symptoms; clinical or diagnostic observations only; intervention not indicated.
- **Moderate (Grade 2)** - Moderate; minimal, local or non-invasive intervention indicated; limiting age-appropriate instrumental activity of daily living.
- **Severe (Grade 3)** - Severe or medically significant but not immediately life-threatening; hospitalization or prolongation of hospitalization indicated; disabling; limiting self-care activity of daily living.
- **Life-threatening (Grade 4)** - Life-threatening consequences; urgent intervention indicated.
- **Death (Grade 5)** - Related to adverse event.

### 7.4.2 Assessment of relationship

All AEs (including SAEs) will be assessed for the relationship of the AE to both pembrolizumab and BGB324 study drug using the following definitions:

- **Not/unlikely related** - The AE is not related if exposure to the investigational product has not occurred, *OR* the occurrence of the AE is not reasonably related in time, *OR* the AE is considered unlikely to be related to use of the investigational product because there are no facts (evidence) or arguments to suggest a causal relationship *AND* there is a possible alternative explanation.
- **Possibly related** - The administration of the investigational product and AE are considered reasonably related in time *AND* the AE could be explained by causes other than exposure to the investigational product.

- **Probably related** - Exposure to the investigational product and AE are reasonably related in time *AND* the investigational product is more likely than other causes to be responsible for the AE *OR* is the most likely cause of the AE.
- **Definitely related** - There is a reasonable temporal sequence between exposure to the investigational product and the AE, *OR* the event follows a known or expected response pattern to the investigational product, *AND* is confirmed by improvement on stopping the dosage of the investigational product. It may also be confirmed by reappearance upon repeated exposure where this is medically and ethically acceptable.

The relationship of the study treatment to an AE will be determined by the Investigator and subsequently reviewed by the Medical Monitor.

For reporting and data analysis purposes, AEs reported with a causality assessment of “Definitely”, “Probably”, and “Possibly” are to be considered as “having a reasonable causal relationship” to study drug. In case of disagreement between the Investigator and the Sponsor’s Medical Monitor, the more conservative assessment will determine the reportability of the case.

#### 7.4.3 Immediate reporting of adverse events and events of clinical interest to the Sponsor

##### 7.4.3.1 Serious adverse events

An SAE is any untoward medical occurrence that at any dose (including overdose):

- Results in death.
- Is life-threatening:
  - “Life-threatening” means that the patient was at immediate risk of death at the time of the SAE; it does not refer to an SAE that hypothetically might have caused death if it were more severe.
- Requires hospitalization or prolongation of existing hospitalization:
  - This means that hospital inpatient admission or prolongation of hospital stay were required for the treatment of the SAE or that they occurred as a consequence of the event.
  - Visits to a hospital by ambulance or to the emergency room without admission will not be regarded as hospitalization unless the event fulfills any other of the serious criteria.
- Results in persistent or significant disability or incapacity:
  - “Persistent or significant disability or incapacity” means a permanent or significant and substantial disruption of a person’s ability to carry out normal life functions.
- Is a congenital anomaly or birth defect.
- Is an important medical event:
  - Medical and scientific judgment should be exercised in deciding whether expedited reporting is appropriate in situations where none of the outcomes listed above occurred. Important medical events that may not be immediately life-threatening or result in death or hospitalization but may jeopardize the patient or may require intervention to prevent one of the other outcomes listed

in the definition above should also usually be considered serious. Examples of such events include allergic bronchospasm requiring intensive treatment in an emergency room or at home, blood dyscrasias, or convulsions that do not result in inpatient hospitalization, or the development of drug dependency or drug abuse.

Note: In addition to the above criteria, AEs meeting either of the below criteria, although not serious per International Conference Harmonisation (ICH) definition, are reportable to the Sponsor in the same timeframe as SAEs to meet certain local requirements.

Therefore, these events are considered serious by the Sponsor for collection purposes.

- Is a new cancer (that is not a condition of the study);
- Is associated with an overdose.

**For the time period beginning when the consent form is signed until treatment allocation, any SAEs, or follow up to a SAE, including death due to any cause other than progression of the cancer under study, that occurs to any patient must be reported within 24 hours to the Sponsor if it causes the subject to be excluded from the trial, or is the result of a protocol-specified intervention, including but not limited to washout or discontinuation of usual therapy, diet, placebo treatment or a procedure.**

**For the time period beginning at treatment allocation through 90 days following cessation of treatment, or 30 days following cessation of treatment if the subject initiates new anticancer therapy, whichever is earlier, any SAE, or follow up to a SAE, including death due to any cause other than progression of the cancer under study, whether or not related to the Sponsor's product, must be reported within 24 hours to the Sponsor either by electronic media or paper.** Electronic reporting procedures can be found in the electronic data capture (EDC) data entry guidelines. Paper reporting procedures can be found in the Investigator Trial File Binder (or equivalent).

Additionally, any SAE, considered by an investigator who is a qualified physician to be related to the Sponsor's product that is brought to the attention of the investigator at any time following consent through the end of the specified safety follow-up period specified in the paragraph above, or at any time outside of the time period specified in the previous paragraph also must be reported immediately to the Sponsor.

All patients with SAE must be followed up for outcome.

#### 7.4.3.2 Events of clinical interest

Selected non-serious and serious AEs are also known as Events of Clinical Interest (ECI) and must be reported to the Sponsor.

**For the time period beginning when the consent form is signed until treatment allocation, any ECI, or follow up to an ECI, that occurs to any subject must be reported within 24 hours to the Sponsor if it causes the subject to be excluded from the trial, or is the result of a protocol-specified intervention, including but not limited to washout or discontinuation of usual therapy, diet, placebo treatment or a procedure.**

**For the time period beginning at treatment allocation through 30 days following cessation of treatment, any ECI, or follow up to an ECI, whether or not related to the Sponsor's product, must be reported within 24 hours to the Sponsor, either by electronic media or paper.** Electronic reporting procedures can be found in the EDC data entry guidelines. Paper reporting procedures can be found in the Investigator Trial File Binder (or equivalent).

**ECIs for this trial include:**

- an overdose of Sponsor's product (either pembrolizumab or BGB324), as defined in [Section 7.8](#), that is not associated with clinical symptoms or abnormal laboratory results.
- an elevated AST or ALT lab value that is greater than or equal to 3X the upper limit of normal and an elevated total bilirubin lab value that is greater than or equal to 2X the upper limit of normal and, at the same time, an alkaline phosphatase lab value that is less than 2X the upper limit of normal, as determined by way of protocol-specified laboratory testing or unscheduled laboratory testing\*

\*Note: These criteria are based upon available regulatory guidance documents. The purpose of the criteria is to specify a threshold of abnormal hepatic tests that may require an additional evaluation for an underlying etiology. The trial site guidance for assessment and follow up of these criteria can be found in the Guidance for Potential Drug-Induced Liver Injury (DILI) Cases Meeting Hy's Law Criteria held in the Investigator Trial File Binder (or equivalent).

## 7.5 Reporting SAEs and ECIs

Adverse events classified as SAEs or ECIs must be recorded on the designated eCRF page and require expeditious handling and reporting to the Drug Safety group at INC to comply with regulatory requirements.

The Principal Investigator (or designee) will notify INC within 24 hours of identifying an SAE or ECI, whether related or unrelated to investigational drug, by completing the SAE form and faxing the eCRF pages and any available supporting documentation to INC (see [Table 19](#) below for contact details).

When an overdose or drug misuse of either of the investigational products occurs with an adverse outcome, the Investigator should only complete the designated AE or SAE eCRF page. Expeditious handling and reported may be appropriate.

In the case of pregnancy, a separate 'pregnancy' and 'pregnancy outcome' form is used. However, the patient should be withdrawn from study treatment and appropriate follow up agreed with the Sponsor.

## 7.6 Assessment of Expected Adverse Events

The Sponsor will assess all SAEs whether they are expected or unexpected. An unexpected AE is any adverse drug event considered to be at least possibly related to BGB324 or pembrolizumab where the outcome, specificity, or severity of which is not consistent with those noted in the current IB for BGB324, or the SmPC or Prescribing Information for pembrolizumab.

## 7.7 Reporting of Pregnancy or Lactation

Although pregnancy and lactation are not considered AEs, it is the responsibility of investigators or their designees to report any pregnancy or lactation in a patient (spontaneously reported to them) that occurs during the trial.

Pregnancies and lactations that occur after the consent form is signed but before treatment allocation/randomization must be reported by the investigator if they cause the patient to be excluded from the trial, or are the result of a protocol-specified intervention, including but not limited to washout or discontinuation of usual therapy, diet, placebo treatment or a procedure.

**Pregnancies and lactations that occur from the time of first dose of study treatment through to 120 days following cessation of Sponsor's product, or 30 days following cessation of treatment if the patient initiates new anticancer therapy, whichever is earlier, must be reported by the investigator.** All reported pregnancies must be followed to the completion/termination of the pregnancy. Pregnancy outcomes of spontaneous abortion, missed abortion, benign hydatidiform mole, blighted ovum, fetal death, intrauterine death, miscarriage and stillbirth must be reported as serious events (as Important Medical Events). If the pregnancy continues to term, the outcome (health of infant) must also be reported.

Pregnancies are to be reported using the same procedures/transmission methods as SAEs: the same fax numbers/email address / same SAE cover sheet. A study specific pregnancy form will be provided for pregnancy reporting.

## 7.8 Definition of Misuse and Overdose

BGB324 overdose is defined as any dose level administered which exceeds the assigned study dose level (including dose reductions).

For this trial, a pembrolizumab overdose will be defined as  $\geq 1000$  mg (5 times the dose) of pembrolizumab. No specific information is available on the treatment of overdose of pembrolizumab. In the event of overdose, the subject should be observed closely for signs of toxicity. Appropriate supportive treatment should be provided if clinically indicated.

If the pharmacy discovers that an overdose has or may have been administered, they should contact the Study Investigator immediately. The Study Investigator will determine if the overdose is an Event of Clinical Interest (see [Section 7.4.3.2](#)).

## 7.9 Investigational Product Complaints

Pharmaceutical technical complaints associated with the investigational product must be reported to the Sponsor immediately. The same reporting timelines as for SAEs apply.

## 7.10 Reporting SAEs to the IRB or IEC

The Investigator must comply with the applicable regulatory requirements related to the reporting of SAEs to the IRB or IEC. All SAEs that are related and unexpected must be reported by the Investigator (or alternative responsible person where specified in study delegation log) to the IEC/IRBs responsible for the study.

In such cases, the Drug Safety group will send the Principal Investigator a Council for International Organizations of Medical Sciences (CIOMS) or MedWatch form describing the event, for them to report to their IEC/IRB.

Other SAEs (i.e. expected or unrelated SAEs) should be reported per the relevant institution's procedures.

The Principal Investigator should also comply with the IEC/IRB procedures for reporting any other safety information. Periodically (at least annually), the IB will be updated to include new and relevant safety information.

Until such time that an AE becomes identified in the BGB324 IB, it should be considered unexpected in regard to BGB324 causality, regardless of whether the AE has been the patient of a previous Safety Update.

## 7.11 Follow Up Information on an SAE

Collection of complete information concerning SAEs is extremely important. Thus, follow-up information that becomes available as the SAE evolves, as well as supporting documentation (e.g. hospital discharge summaries and autopsy reports), should be collected subsequently, if not available at the time of the initial report, and immediately sent using the same procedure as the initial SAE report. The original SAE form(s) must be kept on file at the study site. The Sponsor will also review SAE reports for missing information and send queries to the site for resolution as appropriate.

Appropriate diagnostic tests should be performed and therapeutic measures, if indicated, should be instituted. Appropriate consultation and follow-up evaluations should be carried out by the Principal Investigator (or designee). An SAE is followed until it is considered resolved, returns to baseline, is chronically ongoing, or is explained by the Principal Investigator.

## 7.12 Sponsor Reporting of SAEs

The Sponsor is responsible for reporting serious, study drug-related AEs to the Competent Authorities of the countries participating, the Central IRBs/IECs participating in the clinical trial and to the study Investigators. The Sponsor has assigned the drug safety group at INC Research to act on their behalf for safety submissions on this clinical study.

The Sponsor (or their delegated Medical Monitor) will determine whether expedited reporting is necessary for SAEs depending on the assessment of seriousness, expectedness, and relationship. In case of disagreement between the Investigator and the Sponsor's Medical Monitor regarding causal relationship, the more conservative assessment will determine the reportability of the case.

The Sponsor, or their delegated Clinical Research Organization (CRO), will prepare Development Safety Update Reports (DSUR) and send the DSUR to the European Competent Authority(ies) and the US Authority(ies) where the trial is approved within the regulatory timeframe appropriate for the outcome of their assessment (see [Section 7.12.1](#) and [Section 7.12.2](#)). The assigned CRO will send the DSUR to the concerned IRB/IECs.

### 7.12.1 Expedited reporting

The Sponsor (or delegate) is responsible for the ongoing safety evaluation of the IMP. The assigned drug safety group is responsible for ensuring that expedited reports are made to all concerned Investigators, to the concerned IRB/IECs (where required), and to the relevant regulatory authorities of all adverse drug reactions that are both serious and unexpected, and of findings that could adversely affect the health of patients, impact on the conduct of the trial, or alter the Competent Authority's authorization to continue the trial.

In accordance with the US Code of Federal Regulations, Title 21 CFR Part 312.32, the European Directive 2001/20/EC, and the ICH Guidelines for Clinical Safety Data Management Definitions and Standards for Expedited Reporting, the Sponsor must submit written documentation in the form of an Investigational new drug (IND) Safety Report or suspected unexpected serious adverse reaction (SUSAR) reports, respectively. The Sponsor should submit to the Regulatory Authority all safety updates and periodic reports, as required by applicable regulatory requirements.

The drug safety group will assign a case number to be used in all future correspondence regarding the event.

All events qualifying as IND Safety Reports/SUSARs will be reported to the relevant regulatory authorities, IRB/IECs, and Investigators by the drug safety group. IND Safety Reports/SUSARs are required to be reported within 7 calendar days for life-threatening events and those resulting in death or 15 calendar days for all others. These timeframes begin with the first notification of the IND Safety Reports/SUSARs to the drug safety group from the Investigator.

### 7.12.2 Non-expedited reporting

All SAEs that do not require expedited reporting will be described in the interim safety reports.

## 8 DATA EVALUATION: CRITERIA FOR EVALUATION OF OBJECTIVES

### 8.1 Statistical Considerations, Interim Analysis and Sample Size

The study will employ a  $k$ -stage single arm design, an approach derived from basic statistical theory. If  $p$  denotes the true tumor response rate with drug, the null and alternative hypotheses to be assessed in this trial are:  $H_0 : RR=p_0$  vs  $H_1 : RR=p_1$  ( $p_0 < p_1$ ), with  $p_0=0.20$  and  $p_1=0.35$ . To test these hypotheses, this trial is a  $k$ -stage single arm design with  $k=2$ , being an extension of Simon's 2-stage design. In this design with  $k=2$ , there are two analyses: a single interim and a final analysis. At the interim, the response rate is evaluated in a fixed number ( $m$ ) of patients using a predefined decision rule to determine if the study should stop for futility (in the situation where the null is confirmed) or for efficacy (in the situation where the alternative hypothesis is confirmed). If neither hypothesis is confirmed, a further fixed number of patients ( $l$ ) are assessed for response and a final analysis is performed on all ( $m+l$ ) patients. In both interim and final analyses, the response rate will be presented together with the associated exact 90% confidence interval (CI).

With  $p_0=0.20$  and  $p_1=0.35$ , the interim will be conducted with  $m=28$  patients. If 5 or fewer responses are observed in these 28 patients, the trial will be terminated in favor of the null for futility; however, if 11 or more responses are observed, then the trial will be stopped in favor of the alternative for demonstration of activity. Otherwise a further 28 patients may be evaluated, for a total of 56 patients. If a total of 17 or more responses are seen in 56 patients, then the null will have been rejected in favor of the alternative; otherwise the null will not have been rejected.

Based on 500,000 trial simulations, this design provides an overall power of 80.6% to test the stated null and alternative hypothesis with a 1-sided Type I error rate of 0.048. Under the null hypothesis, the probability of correctly stopping for futility at the interim is 50.2% and, under the alternative hypothesis, the probability of correctly stopping for activity at the interim is 38.4%. Consequently, the expected sample size for the design is 42-44 subjects.

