### Statistical Methods and Sample Size

The trial will follow a  $k$ -stage single arm design with  $k=2$ , being an extension of Simon's 2-stage design. In this design with  $k=2$ , there are two analyses: a single interim and a final analysis. At the interim, the response rate is evaluated in a fixed number ( $m$ ) of patients using a predefined decision rule to determine if the study should stop for futility (in the situation where the null is confirmed) or for efficacy (in the situation where the alternative hypothesis is confirmed). If neither hypothesis is confirmed, a further fixed number of patients ( $l$ ) are assessed for response and a final analysis is performed on all ( $m+l$ ) patients. In both interim and final analyses, the response rate will be presented together with the associated exact 90% confidence interval (CI).

The rationale for a null hypothesis of  $p_0=0.20$  is based on previously published analysis from a clinical trial with pembrolizumab (KEYNOTE-012) in 32 patients with metastatic TNBC (27 patients were evaluable), where an ORR of 18.5% has been observed for pembrolizumab monotherapy. These patients were relatively heavily pre-treated PD-L1 positive patients, with over 50% having received 3 or more lines of therapy.

The ORR of pembrolizumab in combination with BGB324 is expected to be at least as high as this in patients unselected for PD-L1 positive disease.

With  $p_0=0.20$  and  $p_1=0.35$ , the interim will be conducted with  $m=28$  evaluable patients who have the potential for at least 24 weeks (that is, at least 2 on treatment scans) of follow-up. If 5 or fewer responses are observed in up to 28 patients, the trial will be terminated in favor of the null

for futility; however, if 11 or more responses are observed, then the trial will be stopped in favor of the alternative for demonstration of activity. Otherwise, up to a further 28 patients may be evaluated, for a maximum total of 56 evaluable patients. The full study population will have the potential for at least 24 weeks of follow-up. If a total of 17 or more responses are seen in up to 56 patients, then the null will have been rejected in favor of the alternative; otherwise the null will not have been rejected.

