## 8.11 Primary Objectives

Objective response rate as defined by achieving complete response and/or partial response will be presented by percentage rates and 90% CIs. All response assessments will be listed.

Note that the Disease Assessment time point used for this analysis may vary, and need not be the first on treatment assessment. Where there is the possibility of an immune response leading to a false categorization of disease progression, results from later tumor imaging time points may be used for the ORR assessment following the  $k$ -stage design.

Objective response rate is defined as the percentage of patients with a CR or PR (out of the number evaluable), a 90% CI for the overall ORR will be calculated assuming an exact binomial distribution.

A patient who has discontinued both treatments, and subsequently responds having received a subsequent anti-cancer treatment may be excluded (at the statistical analysis) from the subset of responding patients (these patients are evaluable, and will be included in the denominator). Such patients will contribute to the time to progression and death Kaplan Meier plots.

All patients with a documented PR or CR are expected to have the result confirmed by repeat scan at least 4 weeks (28 days) later.

The ORR will further be explored as follows:

- By PD-L1 status (+ve/-ve), using a Chi square or Fishers Exact Test
- By Axl status (+ve/-ve), using a Chi square or Fishers Exact Test, and
- Summarized in a table of PD-L1 by Axl expression status to explore the ORR in each of the four quadrants (++, +-, -+, --). That is, patients will be allocated into one of the 4 groupings: where both Axl and PD-L1 are positive; where there is one positive and one negative and where there are both Axl and PD-L1 negative.

If the PD-L1 expression status is provided as a TPS or, in one of 3 categories usually <1%, 1-49% and  $\geq 50\%$ , the patient will be regarded as PD-L1 positive if their TPS is  $\geq 1\%$ .

A patient with Axl positive disease is defined as one with an expression level of 1+ or greater according to IHC staining intensity, although other cut offs may be considered.

For each patient, the best percentage change in tumor volume will be illustrated in a ‘waterfall’ plot.

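### The planned exact 90% CI and raw ORR ignore the two-stage stopping rule: coverage can fall slightly below 90%, and stage 2 estimates are shifted in both directions, while the decision rule is unaffected

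*Protocol*

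**What the plan says.** Section 8.1 fixes the design with p0 = 0.20 and p1 = 0.35. At the interim, "If 5 or fewer responses are observed in these 28 patients, the trial will be terminated in favor of the null for futility"; and, as the synopsis also states, "if 11 or more responses are observed, then the trial will be stopped in favor of the alternative for demonstration of activity". For 6 to 10 responses, "Otherwise a further 28 patients may be evaluated, for a total of 56 patients". At the end, "If a total of 17 or more responses are seen in 56 patients, then the null will have been rejected in favor of the alternative".

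The operating characteristics are given as follows: "this design provides an overall power of 80.6" per cent, "with a 1-sided Type I error rate of 0.048".

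For estimation, section 8.1 says: "In both interim and final analyses, the response rate will be presented together with the associated exact 90% confidence interval (CI"). Section 8.11 defines the ORR as the plain percentage of evaluable patients who respond, and states the method: "a 90% CI for the overall ORR will be calculated assuming an exact binomial distribution". The protocol mentions no adjustment of the estimate or interval for the stopping rule.

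**The concern.** The total number of responders is binomial only when the sample size is fixed in advance. Here the sample size is 28 or 56 according to the interim count, and the totals seen at 56 come only from trials with 6 to 10 responders in stage 1. A Clopper-Pearson interval computed as if n had been fixed loses its guaranteed 90% coverage, and the raw proportion is no longer unbiased.

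There is no control arm, so the ORR and its interval are what readers will set against the pembrolizumab monotherapy rate of 18.5% cited in the synopsis. At the interim, the same interval goes to the Data Review Committee. Section 8.2.2 asks the committee to document which hypothesis the ORR favors and to make a recommendation that also weighs other data. An interval that seems to say something different from the count rule would be unhelpful there.

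**Working it through.** **Inputs (section 8.1).** p0 = 0.20; p1 = 0.35; stage 1 of 28 with stops at 5 or fewer and at 11 or more; total of 56 with rejection at 17 or more; nominal 90% interval. The rule is treated as binding, with exactly 28 or 56 evaluable patients.

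**1. The plan's own figures.** P(reject) = P(X1 ≥ 11) + Σ over x = 6 to 10 of P(X1 = x)·P(X2 ≥ 17 − x), with X1 and X2 binomial(28, p).
- p = 0.20: 0.0149 + 0.0334 = 0.0483 (stated 0.048).
- p = 0.35: 0.3840 + 0.4215 = 0.8055 (stated 80.6%).
- Futility stop at p = 0.20: 50.05% (stated 50.2%, from simulation). Activity stop at p = 0.35: 38.4% (stated 38.4%).

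The design figures reproduce.

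**2. Coverage of the planned interval.** C(p) is the sum of P(outcome) over all trial-ending outcomes whose Clopper-Pearson 90% interval contains p, using n = 28 for stage 1 stops and n = 56 otherwise.

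| True ORR | Coverage | Bias of raw ORR (points) |
|---|---|---|
| 0.20 | 93.6% | -1.4 |
| 0.25 | 92.6% | -0.8 |
| 0.30 | 89.1% | +0.4 |
| 0.35 | 90.04% | +1.4 |
| 0.40 | 91.6% | +1.7 |

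On a grid in steps of 0.0005 the minimum is 88.4%, at about 0.299. Coverage is below 90% on about 14% of the range 0.20 to 0.35 and about 5% of 0.10 to 0.60. Bias is E(responders / patients) − p.

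**3. Results after stage 2.** For total t, the uniformly minimum variance unbiased estimate (UMVUE) is Σ C(27, x−1)·C(28, t−x) ÷ Σ C(28, x)·C(28, t−x), both sums over x = 6 to 10. The stage-wise interval orders outcomes as futility stops, then stage 2 totals, then activity stops. Its lower limit solves P(this outcome or higher) = 0.05, and its upper limit solves P(this outcome or lower) = 0.05.

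| Result | Raw ORR, planned CI | UMVUE, stage-wise CI |
|---|---|---|
| 12/56 | 21.4% (12.9-32.4%) | 24.8% (13.6-35.0%) |
| 16/56 | 28.6% (18.8-40.1%) | 28.6% (18.8-40.2%) |
| 17/56 | 30.4% (20.4-42.0%) | 29.5% (20.1-41.9%) |
| 20/56 | 35.7% (25.1-47.5%) | 31.7% (23.0-46.4%) |
| 22/56 | 39.3% (28.3-51.1%) | 32.8% (23.7-48.9%) |

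The raw rate is below the UMVUE for totals of 15 or fewer, equal to it at 16, and above it from 17 on. The stage-wise interval kept at least 90% coverage at every rate checked from 0.20 to 0.40.

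**4. Interval against decision.** At trial-ending outcomes the planned lower limit exceeds 0.20 exactly when the null is rejected: 11/28 gives 23.8%, 17/56 gives 20.4% and 16/56 gives 18.8%. Among the counts that continue (6 to 10), 9/28 has a lower limit of 17.9%, but 10/28 gives 20.8-53.0%, which excludes 0.20. This is the only conflict. P(10/28) is 2.4% at a true rate of 0.20 and 15.5% at 0.35.

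**5. Early activity stop.** At a true rate of 0.35, the mean raw ORR given 11 or more of 28 is 44.1%. For stage 1 stops the UMVUE is x/28 and the stage-wise CI equals the planned one (11/28: 39.3%, 23.8-56.5%). Those two methods therefore leave this excess unchanged.

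**The case against.** The strongest defence is that nothing decided in this trial depends on the interval. The counts 5, 11 and 17 decide, their stated error rates are right, and the adjusted interval changes no conclusion. At the boundary of 17/56 the two sets of figures nearly coincide. The coverage shortfall is at most 1.6 points, in narrow bands. The UMVUE is also a trade-off: at a true rate of 0.20 its root mean square error is 7.1 points against 6.8 for the raw rate, although the raw rate does worse at 0.30 and 0.35. Finally, section 8.3 leaves the full description of efficacy analyses to the SAP, which is not shown and could add adjusted estimates.

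Most of this stands and limits the size of the point. It does not remove it, because the protocol itself names the unadjusted method.

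Three stronger readings are tempting, and the documents do not support them.
- **Inflated type I error.** Under the null, the chance that a displayed interval excludes 0.20 at either look is 6.5%, against 4.8%. The extra 1.6 points are exactly the trials with 10/28 at the interim and fewer than 17/56 at the end. That is a display in a continuing trial that does not go on to reject. The error rate of the rule stays at 4.8%.
- **Raw figures always too favorable.** At a true rate of 0.20 the raw ORR is biased downward, and it lies below the UMVUE for small stage 2 totals.
- **Coverage generally below 90%.** It is at least 90% at both design values.

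**Conclusion.** The point holds as one about estimation and reporting. The interval that sections 8.1 and 8.11 call exact is exact only for a fixed sample size. Under the actual rule its coverage can fall to about 88.4%, and the raw ORR carries a bias of about -1.4 to +1.7 points overall. The differences that a reader would notice are in stage 2 results away from 16 or 17 responders: 4.0 points at 20/56 (35.7 − 31.7) and 6.5 points at 22/56 (39.3 − 32.8), against a design difference of 15 points. The design, its error rates and its decisions are sound.

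These figures assume that the stopping rule is followed as written and that the evaluable numbers are exactly 28 and 56. Sections 8.1 and 8.2.2 leave some discretion over continuing. If it is used, the sampling distribution changes and the figures become approximate.

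**What to change.** In sections 8.1 and 8.11 (or in the SAP, with a cross-reference), before interim data are seen:

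1. If the trial goes to 56 patients, report a design-adjusted estimate, with the choice between UMVUE and median-unbiased fixed in advance. Give it a 90% CI from stage-wise ordering of the two-stage sample space. Keep the raw ORR and Clopper-Pearson CI beside it, named as unadjusted.
2. If the trial stops at stage 1, the UMVUE and stage-wise CI equal the planned figures. State in the report that an estimate after an early activity stop tends to be too high (mean 44% if the truth is 35%).
3. State that the interim CI is descriptive and that only the counts 5 and 11 decide. Do not add a separate, wider interim interval matched to the 11/28 boundary (one-sided 0.0149, about a 97% CI). At 11/28 its lower limit would be 20.0% against 23.8% for the stage-wise 90% CI, which leaves two intervals for one result.

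The cost is a few sentences and a few lines of code. The downside for the sponsor is somewhat less favorable figures for high totals at 56. The final decision is unchanged: the adjusted lower limit is 20.1% at 17/56 and 18.8% at 16/56.
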